8. DATA ANALYSIS

8.1 Demographic Data

Analytical results will not take demographic data into account.

8.2 Laboratory Methods

The EDTA sample will be processed on the HemoScreen POCT analyser for FBC including 5 part differential.

The EDTA sample will be then be sent to the laboratory and processed on the Sysmex XN1000 for FBC including 5 part differential.

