Recently, POCT devices that measure FBC at the patient bedside have become available for clinical use and as such provide the potential to reduce the risk of clot formation. Currently, there are only two commercial POCT devices available for FBC measurement, both of which are not clinically validated for the age group from 0-3 months old. The HemoScreen is one of the two devices, which has a small footprint, requires a small sample of capillary or venous blood (40µL in each capillary) and gives 20 FBC results in 5 minutes across the 5-part differential. This device however, has only been clinically validated for patients 2 month old and onward. To realise the full potential of HemoScreen POCT device, it needs to be clinically validated in neonates < 2months old.

Although, HemoScreen POCT device is CE marked and clinically validated in the age group of > 2 months old onward. It is important to mention that HemoScreen is reasonably new to the healthcare market; hence, clotting studies for the <2 months old are not available yet.

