5.2 Secondary Objectives

To determine whether the device could offer a solution for the clinical issue of clotted samples from this population group.

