7.3 Sample Collection

The sample collection, analysis and storage is outlined below:

1. When the patient's clinical care requires a FBC result, the sample will be collected with from the baby's heel (capillary) or as a venous sample into a purple topped paediatric EDTA tube. The standard quantity that is collected for this analysis is 400µL.
2. The sample will then be mixed to ensure dispersion of the EDTA anticoagulant through the blood and to ensure an even distribution of blood products. From this sample, 40µL will be drawn from the blood that has collected from the lid of the sample into the HemoScreen capillary sample collection device. The sample collection device will be placed into the HemoScreen cartridge and processed on the analyser by a trained user.
3. The FBC and 5 part differential results will be stored on the analyser and collected by the principal investigator. The clinical team will not report or act on these results.
4. The remaining sample will be labelled up and sent to the laboratory with a request card for FBC analysis.
5. The Laboratory sample will be processed as usual on the Sysmex XN1000 for FBC including 5 part differential.
6. The results will be reported to the clinical team for clinical management. The EDTA sample will be stored in the laboratory for a few days and then disposed as per normal laboratory procedure.

7. The laboratory results will be statistically compared to the retrieved results from HemoScreen (using Altman Bland and Passing Bablock Regression).

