8.6 Termination Criteria

A clotting rate of 10% on the Hemoscreen will result in the early termination of the study. The study will run until we have collected 30 suitable samples. Once we have the data from 30 samples the trial will close

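### The clotting objective is wider than the specimen route can answer: HemoScreen is run only on blood from a filled, mixed EDTA tube, so only clotting after tube collection is informed

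*Protocol*

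**What the plan says.** Section 7.3 (Sample Collection) gives one specimen route, in this order:

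- Collection: "the sample will be collected with from the baby's heel (capillary) or as a venous sample into a purple topped paediatric EDTA tube". The standard volume is given as 400 µL.
- Mixing: "The sample will then be mixed to ensure dispersion of the EDTA anticoagulant through the blood".
- HemoScreen aliquot: "From this sample, 40µL will be drawn from the blood that has collected from the lid of the sample into the HemoScreen capillary sample collection".
- Laboratory: "The remaining sample will be labelled up and sent to the laboratory with a request card for FBC analysis", where it is run on the Sysmex XN1000.

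Section 8.2 (Laboratory Methods) repeats the first test in short form: "The EDTA sample will be processed on the HemoScreen POCT analyser for FBC including 5 part differential". No section describes blood going straight from the heel into the HemoScreen capillary.

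Three other places depend on this route. Section 4 says that bedside devices "provide the potential to reduce the risk of clot formation". Section 5.2 sets the secondary objective: "To determine whether the device could offer a solution for the clinical issue of clotted samples from this population group". Section 8.6 adds a rule on the study itself: "A clotting rate of 10% on the Hemoscreen will result in the early termination of the study".

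**The concern.** Section 4 does not settle where clots arise. It links platelet activation to the heel prick, reports a higher clotting risk with capillary collection, and lists both transfer time and collection technique among the postulated causes. It adds that no study has yet explained the main reason.

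The HemoScreen aliquot is drawn after the tube has been filled and mixed, so a clot formed during collection is there before either analyser is used. The design cannot show that the device avoids such a clot, because the device is not given the chance. Section 5.2 nevertheless asks about clotted samples in general. Sections 5.1 and 14 carry the result forward to a larger CE-marking study of the device without naming the route that was tested.

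The result could mislead in either direction. A high HemoScreen clotting rate could count against the device, and end the study under 8.6, partly because of clots that were already in the tube. A low rate could be read as evidence for direct bedside sampling, which was not done.

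**Working it through.** **1. Which steps are shared.** Setting section 7.3 beside the causes named in section 4:

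| Step | HemoScreen | Laboratory | Can the design separate it? |
|---|---|---|---|
| Skin puncture or venous draw | same | same | no |
| Filling the EDTA tube | same | same | no |
| Mixing with EDTA | same | same | no |
| Transfer to the laboratory | avoided | present | yes |
| Wait before laboratory analysis | avoided | present | yes |

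Of the two process causes in section 4, transfer time falls where the two tests differ. Collection technique falls where they are identical.

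**2. What a pair of results can mean.** The aliquot is 40 of 400 µL, or 10% of the standard volume, and leaves 360 µL.

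- Both clotted: at least one clot was there before the aliquot was drawn. The device could not have prevented it in this design.
- Laboratory clotted, HemoScreen not: the clot formed after the aliquot was drawn, or it was already in the tube and the aliquot missed it.
- Neither clotted: nothing is learned about collection clots under another route.

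So the pattern that favours HemoScreen points to post-collection clotting, but does not prove it. No pattern speaks to direct heel-to-cartridge sampling.

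**3. How much the 10% rule could be affected.** Let p be the clotting rate of the whole tube, s the share of clots formed before the aliquot is drawn, and h the chance that the lid aliquot inherits such a clot. The HemoScreen rate due to clots already in the tube is

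q = p × s × h.

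Section 4 quotes 20-30% for p, from neighbouring units in large teaching hospitals. The documents give neither s nor h, and each can lie between 0 and 1. Hence q lies between 0 and 20% (if p = 20%) or between 0 and 30% (if p = 30%). The 10% level falls inside both ranges, so the documents do not show whether clots already in the tube would matter to the rule.

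To show the sensitivity, take 10% to mean at least 3 clotted out of 30 samples, counted once at the end, with samples treated as independent. These are assumptions, because section 8.6 states no denominator and a baby may give two samples. The exact binomial chance of meeting the rule from clots already in the tube alone is:

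| q | P(3 or more of 30) |
|---|---|
| 0% | 0 |
| 5% | 0.19 |
| 10% | 0.59 |
| 15% | 0.85 |
| 20% | 0.96 |
| 30% | 0.998 |

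The table does not say which row applies.

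**4. The opposite result.** With 0 of 30 HemoScreen samples clotted, the upper end of the exact two-sided 95% interval is 1 − 0.025^(1/30) = 11.6%. That limit applies to aliquots from a filled EDTA tube and to no other route.

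**The case against.** The case for the protocol has several good parts.

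- **The same-tube split is right for agreement.** Both analysers measure the same blood, and no blood is taken beyond the clinical sample. This stands, and the split should be kept.
- **Capillary blood is tested, and before transport.** A reader might infer that the trial does not test bedside capillary use at all, or that the clotting objective cannot be answered. The documents support neither. Section 7.3 allows heel blood and takes the HemoScreen aliquot before the tube leaves, so clotting in transfer and delay is within reach.
- **Direct heel fill is not stated to be the intended use.** Section 4 ties the hoped-for benefit to measurement at the bedside and gives the 40 µL volume as a separate feature of the device. A reader might infer that the wrong mode of use was tested, but no section says so.
- **A lid aliquot need not inherit a clot.** This stands. It rules out any firm figure for the number of clots already in the tube that reach HemoScreen, and any fixed ceiling on the benefit the design could show. The quoted 20-30% is also not from this unit, and venous samples, which section 4 says clot less, are allowed.
- **The claims are modest.** Section 5.2 asks only what the device could offer, and section 14 calls this a pilot that needs a larger study. This softens the point but does not remove it. The primary objective is the decision on that larger study, and the specimen route behind the decision is not named in the objectives or in section 14.

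**Conclusion.** The point holds as a mismatch between specimen route and clotting objective. Under 7.3 and 8.2 the design can inform 5.2 only for clots that form after tube collection. It cannot show whether direct heel-to-cartridge sampling would avoid clots formed during collection. This follows from the order of steps and needs no numerical assumption.

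The effect on the 10% rule in 8.6 is possible but of unknown size. At the quoted background rate, the HemoScreen clotting rate due to clots already in the tube could be anywhere from 0 to 20-30%. A reader might infer that such clots are likely to stop the study. The documents do not support that, because they give neither the share formed at collection nor whether a lid aliquot would carry them.

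The agreement comparison and its success criterion in 8.5 do not concern clotting and are not affected. The correction is worth making because it changes what the trial may conclude, at almost no cost.

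**What to change.** - Limit section 5.2, and the conclusions drawn under 5.1 and 14, to HemoScreen run at the bedside from a filled EDTA tube before transport.
- State that a high or low HemoScreen clotting rate, including a stop under 8.6, does not speak for or against direct capillary sampling.
- Record for each sample the times of collection, HemoScreen run and laboratory run, so that post-collection clotting can be described against delay.
- Keep the same-tube split for the agreement analysis, and leave 8.5 unchanged on this account.

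The cost is a few sentences and three times per sample, with no extra blood and no extra patients. The downside is a narrower claim.

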8.3 Analytical Results

The analytical results will be returned to the Investigator in electronic format. Statistical analysis will be performed using Analyse-it add-in package for Microsoft Excel.

8.4 Spurious Data

Extreme values “outliers” will be ruled out using Box-Cox statistical test.

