7.4 Target recruitment

A minimum of 15 patients are to be recruited to make a library of a minimum of 30 samples (max. 2 samples per single patient) is recommended by Altman and Bland graphical method as described in the Lancet 1986³⁷. This sample size would give a 95% Confidence Interval (CI) of about +/- 0.34S, where S is the standard deviation of the difference of the two methods used in this study (HemoScreen and Sysmex).

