8.5 Successful Criteria

The comparison will be considered successful if a minimum of 95% of HemoScreen results for all parameters are within 2SD (Standard Deviations) from the Laboratory (Sysmex XN1000).

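### Section 8.4 excludes extreme values by Box-Cox, which cannot identify outliers; exclusions would be ad hoc and, if made on paired differences, would overstate agreement

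*Protocol*

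**What the plan says.** Section 8.4 is a single sentence under the heading "8.4 Spurious Data": extreme values "will be ruled out using Box-Cox statistical test". It gives no cut-off, does not say whether raw results or paired differences are examined, asks for no analytical cause, and plans no analysis with the values kept.

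The data that remain feed two things:

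- Section 7.3, step 7, compares the analysers "using Altman Bland and Passing Bablock Regression".
- Section 8.5 declares success if "a minimum of 95% of HemoScreen results for all parameters are within 2SD (Standard Deviations) from the Laboratory (Sysmex XN1000").

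Section 7.4 plans "a library of a minimum of 30 samples (max. 2 samples per single patient") and defines the scale of disagreement: "S is the standard deviation of the difference of the two methods used in this study". Section 5.1 makes the comparison the basis for deciding whether the device goes forward to a larger CE-marking study. Section 8.6 closes the study once thirty usable samples are in hand, without saying whether a pair excluded under 8.4 is replaced.

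**The concern.** There are two problems, of different certainty.

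The first is plain from the text. Box-Cox chooses a power (lambda) that brings a distribution closer to Normal. It does not test single values. The protocol fixes a method that cannot do what is asked of it, so this is more than detail left to an analysis plan. Whoever carries out 8.4 must invent a rule, possibly with both analysers' results in view.

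The second depends on how the invented rule is applied. In a method-comparison study, a gross discrepancy between the new device and the laboratory is evidence about the device. Removing it because it is extreme, with no fault identified, makes S smaller, narrows the limits of agreement and makes the 8.5 criterion easier to meet. The go/no-go decision would then lean towards go.

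**Working it through.** **Inputs from the protocol.** 30 paired samples (7.4); success if at least 95% lie within 2SD (8.5); S is the SD of the between-method differences (7.4); 20 results per sample (section 4).

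**Assumptions, not in the protocol.** The frequency and size of gross errors; independent pairs, although up to two may come from one patient; and, for the simulation, Tukey fences (1.5 × IQR) on the differences as a stand-in rule, since Box-Cox supplies none.

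**The plan's own figure.** Section 8.4 gives no number. The only design figure is the "95% Confidence Interval (CI) of about +/- 0.34S" in 7.4. At n = 30 the half-width is 1.96/√30 = 0.36S for the mean difference and 1.96 × √(3/30) = 0.62S for a limit of agreement; 0.34S is the limit-of-agreement value at n = 100. The stated figure therefore does not reproduce at 30, but that does not decide this point. What matters here is that precision is expressed in S, the quantity that trimming shrinks.

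**Step 1: effect on the limits of agreement.** Let a share f of differences be displaced by 5S, where S is the SD of the ordinary differences.

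- Errors balanced in sign: SD = S√(1 + 25f).
- Errors all in one direction: SD = S√(1 + 25f(1 − f)).
- Understatement of width if the displaced values are removed: 1 − S/SD.

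| Gross errors | SD, balanced | Understated | SD, one-sided | Understated |
|---|---|---|---|---|
| 1 in 30 | 1.354S | 26% | 1.344S | 26% |
| 3 in 30 | 1.871S | 47% | 1.803S | 45% |

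**Step 2: effect on the success count, one parameter.** 0.95 × 30 = 28.5, so 29 must be inside: 29/30 = 96.7% passes and 28/30 = 93.3% fails. Example: 28 ordinary differences (SD 0.83, largest 1.75) plus two at +5, with a fixed band of ±2.

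- All kept: 28/30 inside, fail. SD 1.50, limits of agreement −2.61 to 3.27.
- Two removed: 28/28 inside, pass. SD 0.83, limits −1.63 to 1.63.

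This reversal needs the fixed band. If 2SD is recomputed after removal, the band is ±2 × 0.83 = ±1.66, the two values at ±1.75 fall outside, and 26/28 = 92.9% still fails. The limits of agreement narrow in either case.

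**Step 3: chance of passing, one parameter.** 30 independent pairs, 40,000 simulated studies, all pairs kept versus Tukey outliers removed. Gross errors have five times the ordinary SD.

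| Share of gross errors | Fixed 2SD: kept / removed | 2SD recomputed: kept / removed |
|---|---|---|
| 0% | 0.60 / 0.74 | 0.67 / 0.75 |
| 5% | 0.31 / 0.67 | 0.63 / 0.73 |
| 10% | 0.14 / 0.60 | 0.48 / 0.71 |

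Repeat runs differ by about 0.01. At 5% contamination the gain is about 35 points with a fixed 2SD and about 10 with a recomputed one. The direction is the same in every row. The mean SD of the differences falls from 1.40 to 0.97 at 5% and from 1.74 to 1.00 at 10%.

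**The case against.** The error in naming Box-Cox has no good defence. Reading the sentence as a check for outliers does not help, because Box-Cox cannot check for them either, and the section heading points to exclusion. The case on the other side concerns the consequences, and much of it stands.

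- **Values or differences.** A reader might infer that the protocol orders the removal of extreme differences. It does not say so; it speaks of extreme values. Applied to raw counts, the rule would drop very high or low results on which both analysers may agree. That loses the most abnormal neonatal results and narrows the range tested, but it does not systematically delete disagreement.
- **Which SD.** Section 8.5 does not define its SD. If it is recomputed from the analysed differences, trimming also tightens the band, and the gain in passing is much smaller.
- **Per parameter or pooled.** A reader might infer that only one discordant result is allowed. That holds if each parameter is judged separately. Pooled, there are 20 × 30 = 600 results and 30 may lie outside, so two deletions would rarely change the verdict.
- **Replacement.** If excluded pairs count as unusable under 8.6, they may be replaced, and the denominator would not be 28.
- **Passing-Bablok.** It is rank-based and resists a few outliers, so that part of the comparison is little affected by removing them.
- **Legitimate exclusions.** Dropping a clotted sample or a flagged analyser failure is sound practice. The protocol does not limit exclusion to such cases.

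The study is also a pilot whose device results are withheld from care and which a larger validation must follow. That lowers the stakes, but the pilot's product is the decision to go forward.

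**Conclusion.** The point holds in two parts. Without condition: 8.4 names a transformation as an outlier test, cannot be carried out as written, and leaves exclusions ad hoc with no assignable cause required.

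Conditionally: if exclusions are made on paired differences or on grossly wrong HemoScreen values, agreement is overstated. The limits of agreement would be understated by about 26% with one, or 45-47% with three, results in 30 displaced by 5S; both the error size and the frequencies are assumed. The chance of meeting 8.5 rises under either reading of 2SD, by much less when 2SD is recomputed. The change from 28/30 to 28/28 illustrates what can happen under a fixed 2SD, per-parameter counting and no replacement; it is not a prediction.

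The protocol does not support the stronger inference that the primary result will be biased or that two deletions will reverse it. It leaves open what the rule acts on, which SD applies, how results are counted and whether pairs are replaced.

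**What to change.** Replace section 8.4 with wording such as:

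> All valid paired results are kept in the primary analysis and in the success count. A pair is excluded only for a documented analytical or pre-analytical failure (for example device error flag, insufficient volume, clot), recorded before the two results are compared. Every exclusion is listed, and clots still count towards the clotting rate in 8.6. Results without values flagged by a named outlier test on the paired differences (for example generalised ESD) are shown as a sensitivity analysis only.

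If Box-Cox is kept, use it only to choose a scale for the Bland-Altman analysis. Other policies with a valid named procedure and an assignable-cause requirement would also correct the error; this one keeps the primary result free of judgement about extremes. It does not settle the undefined 2SD in 8.5.

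The cost is a change of wording and one extra analysis. The limits of agreement may come out wider.

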8.5 Successful Criteria

The comparison will be considered successful if a minimum of 95% of HemoScreen results for all parameters are within 2SD (Standard Deviations) from the Laboratory (Sysmex XN1000).

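### Section 8.5 does not say whether the 95% success criterion is pooled over all parameters or must be met by each one, and the two readings can give opposite verdicts

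*Protocol*

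**What the plan says.** The only success rule is in Protocol section 8.5: "a minimum of 95% of HemoScreen results for all parameters are within 2SD" of the Sysmex XN1000 result. The comparison itself is clear, HemoScreen against the laboratory analyser, and section 7.3 names Bland-Altman and Passing-Bablok as the methods. Neither section says how results from different parameters combine into the 95%, and no parameter is named as deciding.

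Two other statements fix the size of the problem. Section 4 says that the device "gives 20 FBC results in 5 minutes across the 5-part differential". Section 8.6 says: "The study will run until we have collected 30 suitable samples". Section 7.4 adds that the 30 samples come from at least 15 patients, with at most two samples each.

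The SD in the 2SD limit is not defined in section 8.5. The only SD defined anywhere is in section 7.4, where S is the standard deviation of the between-method difference.

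**The concern.** The phrase about all parameters has two natural readings. It can mean one proportion taken over every result of every parameter, or a proportion that each parameter must reach. Sections 5.1, 7.3, 7.4 and 8.1 to 8.4 do not settle which.

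The rule serves the primary objective, whether the device merits a larger CE-marking study. Under the pooled reading, parameters that agree easily can offset one that does not, so a poorly measured parameter may not show in the verdict. Under the strict reading with 20 parameters, chance alone will usually fail a device that agrees well. As the protocol stands, the same data can be called a success or a failure, and the reading could be chosen after the results are retrieved.

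**Working it through.** **Inputs from the Protocol.** 20 results per sample (section 4); 30 samples (sections 7.4 and 8.6); threshold at least 95% (section 8.5). The protocol gives no error rate or pass probability for the success rule, so there is no stated figure to reproduce. The ±0.34S in section 7.4 concerns the precision of the method comparison and does not enter here.

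**Assumptions, not in the Protocol.** The limit is centred on the laboratory value. True agreement per result is 98% or 99% for a well-measured parameter and 50% for a poor one. Results within a sample have correlation 0, 0.5 or 0.8 (Gaussian latent variable, 20,000 simulated studies). Samples are treated as independent, which ignores the two-per-patient pairing. The number of parameters with a Sysmex counterpart is not stated, so 20, 15 and 10 are shown.

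**Step 1: thresholds.**
- Pooled: 20 × 30 = 600 results; 0.95 × 600 = 570 needed; 30 misses allowed. With 15 parameters, 428 of 450 (22 misses). With 10, 285 of 300 (15 misses).
- Per parameter: 0.95 × 30 = 28.5, so 29 of 30, since 28/30 = 93.3%.

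**Step 2: can pooling mask a poor parameter?** One parameter is within limits 50% of the time, so about 15 misses are expected from it. Probability that the pooled rule declares success:

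| Comparable parameters | Agreement of the others | Correlation 0 | 0.5 | 0.8 |
|---|---|---|---|---|
| 20 | 99% | 0.995 | 0.95 | 0.89 |
| 20 | 98% | 0.83 | 0.73 | 0.70 |
| 15 | 99% | 0.83 | 0.78 | 0.76 |
| 10 | 99% | 0.25 | 0.30 | 0.34 |

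Under the per-parameter rule the poor parameter alone would need at least 29 of 30 at 50%, with probability 31 × 0.5^30 ≈ 3 × 10⁻⁸, so success is effectively zero in every row.

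**Step 3: does requiring every parameter work?** For one parameter with true agreement p, P(at least 29 of 30) = p^30 + 30 p^29 (1 − p).
- p = 0.98: 0.545 + 0.334 = 0.879. All 20, if independent: 0.879^20 ≈ 0.077.
- p = 0.99: 0.740 + 0.224 = 0.964. All 20: ≈ 0.48.

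The pooled rule passes the same uniform 98% device with probability 1.00, 0.99 and 0.94 at correlation 0, 0.5 and 0.8. Requiring all 20 gives about 0.08, 0.23 and 0.44.

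**Step 4: a short deciding set.** With four parameters at 29 of 30 each, independent: 0.879^4 ≈ 0.60 at 98% agreement and 0.964^4 ≈ 0.86 at 99%.

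**The case against.** **The per-parameter reading may be what is meant.** Bland-Altman and Passing-Bablok are run one analyte at a time, and an SD of differences has a different unit for each parameter. Both favour the reading in which each parameter must pass, and under it no masking occurs. This stands, so the defect is ambiguity and not a pooled rule as such. That reading brings the failure shown in step 3, however, so it does not rescue the section.

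**A reader might infer that one parameter could fail in every infant and the study still succeed.** The documents do not support this as a realistic outcome. It needs exactly 20 comparable parameters and no miss among the other 570 results, which has probability 0.99^570 ≈ 0.003 at 99% agreement. With 19 parameters only 28 misses are allowed, so it cannot happen. Section 4 counts device outputs and does not say that all 20 have a laboratory counterpart. A reader might also infer that a clinically essential parameter is the one at risk, but the protocol ranks none.

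**The masking depends on what the SD is.** If 2SD is taken about the mean of the differences using their own SD, at most 25% of a parameter's results can lie outside (Chebyshev), and about 4% would under normality whatever the bias. The 50% scenario is then impossible. The wording "within 2SD (Standard Deviations) from the Laboratory (Sysmex XN1000") points to a limit centred on the laboratory value, but the SD remains undefined.

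**A statistical analysis plan might name the parameters, and this is a pilot.** A plan may exist. But the protocol itself fixes the decision rule, and fixes it in a form that can be read two ways. The pilot setting limits the stakes: HemoScreen results are not used for care, and section 14 requires a larger study before clinical use.

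**Conclusion.** The point holds as an ambiguity in the study's only success rule, with poor performance under either reading.

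- **Pooled, with 20 comparable parameters:** a parameter outside limits in about half the samples is masked with probability about 0.89 to 0.995 if the others agree 99% of the time, and 0.70 to 0.83 if 98%. The effect weakens with fewer parameters: at 99%, about 0.76 to 0.83 with 15 and 0.25 to 0.34 with 10.
- **Per parameter, all 20 required:** a device with 98% agreement on each passes only about 8% of the time if results are independent, and 0.23 to 0.44 of the time at correlation 0.5 to 0.8.

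The thresholds follow from the Protocol's own 20, 30 and 95%. The probabilities rest on illustrative agreement rates and correlations, and the masking figures also need a limit centred on the laboratory value. The correction should be made before results are retrieved from the device.

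**What to change.** In section 8.5:

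1. State that the proportion within limits is computed separately for each parameter and is never pooled across parameters.
2. Name, before data retrieval, a short set of deciding parameters chosen by the investigators, each of which must meet the criterion. Report all other parameters descriptively, outside the verdict.
3. Define the SD in the 2SD limit: whose it is, how it is obtained, and whether the limit is centred on the laboratory value or on the mean difference.
4. State the pass probability of the chosen rule.

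This takes a few sentences and no extra samples or measurements. The investigators must commit in advance to the deciding parameters, and a device with one poor deciding parameter can no longer be called successful.

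There is also a false-failure cost. With four deciding parameters at 29 of 30 each, a device with 98% true agreement would fail about 40% of the time (1 − 0.60) and one with 99% about 14% (1 − 0.86), independence assumed. If that is too high for a pilot, the number of deciding parameters or the per-parameter threshold should be reconsidered now, not after the data are seen.

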5. OBJECTIVES

5.1 Primary Objectives

To ascertain whether the device is suitable for a larger scale CE marking research project to enable clinical use of the device in neonates< 2months of age.

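### The 2SD in the success criterion is undefined and tied to no allowable difference, and no plausible reading of it gives a sound test of agreement

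*Protocol*

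**What the plan says.** Section 8.5 (Successful Criteria) requires that "a minimum of 95% of HemoScreen results for all parameters are within 2SD (Standard Deviations) from the Laboratory (Sysmex XN1000". No parameters are listed and the SD is not defined.

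The only SD defined in the protocol is in section 7.4 (Target recruitment), in a statement about precision: "where S is the standard deviation of the difference of the two methods used in this study (HemoScreen and Sysmex". The same section plans "to make a library of a minimum of 30 samples (max. 2 samples per single patient".

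Section 7.3 (Sample Collection) names the comparison methods, "using Altman Bland and Passing Bablock Regression", and attaches no acceptance limit to either. Section 4 (Background and Rationale) says that the device "gives 20 FBC results in 5 minutes across the 5-part differential".

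The primary objective in section 5.1 is "To ascertain whether the device is suitable for a larger scale CE marking research project". Section 14 makes a larger multi-centre study conditional on success.

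**The concern.** An agreement study needs a yardstick that says how far the new device may lie from the laboratory before the difference matters. Section 8.5 uses a multiple of an unnamed SD instead. If that SD is estimated from the same paired differences that are being judged, a worse device widens its own limits. If it is some other SD, the rule may be far too easy or far too hard. The wording about all parameters adds a second ambiguity: each parameter may have to reach 95%, or 95% of all results pooled may be enough.

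This is the only acceptance limit for agreement in the protocol, so it effectively decides the primary objective. While the SD and the combining rule are open, the same data can give a pass or a fail, and the reading could be chosen after the results are known.

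**Working it through.** **Inputs.** 30 samples and S, the SD of the differences (section 7.4); the 95% threshold and 2SD (section 8.5); 20 parameters (section 4, taken as an assumption because 8.5 lists none). Normal errors and independent samples are assumed, which ignores that one infant may give two samples.

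**The plan's own figure.** Section 8.5 gives no pass probability to reproduce. The nearest figure is the "95% Confidence Interval (CI) of about +/- 0.34S" of section 7.4. At n = 30 a limit of agreement has half-width 1.96 × √(3/30) × S = 0.62S, and the mean difference has 1.96/√30 × S = 0.36S, so neither gives 0.34S. That mismatch is a separate matter and nothing below depends on it.

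**Threshold.** 0.95 × 30 = 28.5, so at least 29 of 30 must lie inside; 28/30 = 93.3% fails.

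**Pass probability for one parameter, by meaning of SD.** Readings (a) to (c) are simulated with at least 100,000 runs per setting.

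(a) *S, centred on the mean difference.* Count |d − mean(d)| ≤ 2S. Both sides scale with the scatter and the bias cancels. On average 96.0% lie inside, and P(at least 29/30) is 0.67 to 0.68 with the SD of the differences set to 0.1, 1, 10 or 100. The result carries no information on agreement.

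(b) *S, measured from zero difference.* Count |d| ≤ 2S. P = 0.61, 0.51, 0.27, 0.01 and 0 at a bias of 0, 0.25, 0.5, 1 and 2 SD. The rule sees bias relative to scatter but not the size of the scatter. A very noisy unbiased device passes 61% of the time, while a precise device whose small constant offset is large relative to its scatter fails.

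(c) *Between-infant SD of the Sysmex results.* Count |d| ≤ 2 × SD(Sysmex).
- A device that always returns the cohort mean: 96.0% inside, P = 0.67 (the same algebra as (a)).
- Bias of 1 between-infant SD, error SD 0.3 of it: P = 0.96.
- Bias 1, error SD 0.5: P = 0.71.
- Bias 1.5, error SD 0.3: P = 0.49.
- Bias 2, error SD 0.3: P = 0.04.
- No bias, error SD 0.5: P = 1.00; error SD 1: P = 0.55.

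The rule responds to agreement here, but leniently.

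(d) *Fixed analytical SD of the Sysmex, σ.* With no bias and an SD of differences of kσ, the share inside is q = 2Φ(2/k) − 1, and P = q³⁰ + 30 q²⁹(1 − q).
- k = 0.75: q = 0.992, P = 0.978.
- k = 1: q = 0.954, P = 0.601.
- k = 1.41: q = 0.843, P = 0.039.
- k = 2: q = 0.683, P = 0.0002.

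Two unbiased analysers that both have imprecision σ give k = √(1 + 1) = 1.41, so an analyser as good as the laboratory's would fail a parameter about 96% of the time.

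**Combining parameters.** If each of 20 must pass and they are independent, P(all) = P²⁰, with P from the binomial formula in (d) and q the true within-limit rate.
- q = 97%: 0.773²⁰ = 0.006.
- q = 99%: 0.964²⁰ = 0.48.
- q = 99.9%: 0.9996²⁰ = 0.99.

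Under reading (a), all 20 pass with probability about 0.0004 if independent, 0.002 at correlation 0.6 and 0.07 at correlation 0.9. If results are pooled instead, parameters that agree well can hide ones that do not.

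**The case against.** A reader might infer that the criterion is met or missed regardless of whether the devices agree, because the study data supply the SD. The protocol does not support that as a general statement. Section 8.5 does not say where the SD comes from, and S is defined in 7.4 for another purpose. The wording of 8.5 speaks of distance from the laboratory, which fits measurement from zero better than from the mean difference. Only reading (a) is fully circular. Bias matters under (b), and agreement matters under (c) and (d).

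A reader might also infer that the demand on all parameters makes failure nearly certain even for a good device. That depends on the true within-limit rate: success is very unlikely at 97% but has probability 0.99 at 99.9%. The count of 20 comes from a description of the device, and blood-count parameters are unlikely to be independent.

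It can be added that the study is a pilot, that its HemoScreen results do not guide care, that the Bland-Altman and Passing-Bablok analyses will show bias and scatter, and that definitions could sit in a statistical analysis plan.

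These points limit how broadly the defect can be stated, but they do not remove it. The named analyses carry no acceptance limit, and the 10% clotting rule in 8.6 concerns stopping. The protocol itself fixes the success rule, and the rule works badly on every reading examined, including the one most favourable to it, (d).

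**Conclusion.** The point holds in conditional form. The SD, the centring and the combining rule in section 8.5 are undefined and no allowable difference is given. Of the four plausible readings, one is circular (pass probability about 0.67 at any bias or scatter), one is blind to the absolute size of the scatter, one is lax, and one would fail an equally precise, unbiased analyser about 96% of the time for a single parameter. Applied to all parameters, the chance of success runs from almost none to almost certain, depending on the reading and the true within-limit rate. A go/no-go decision taken on this rule would be unsound, so it should be changed before the first sample.

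The figures rest on Normal errors, 30 independent samples and 20 parameters. Section 8.4 says that extreme values "will be ruled out using Box-Cox statistical test" and does not say whether this happens before the success check. Removing them first could shift the pass rates; that effect was not quantified.

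**What to change.** Rewrite section 8.5 so that, before the first sample:

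- each parameter has an allowable difference from the laboratory value, set outside the study data (for example from the laboratory's own performance specification);
- agreement is the share of paired differences within that limit, measured from the Sysmex value;
- a verdict is given for each parameter;
- the rule that combines these into the overall verdict is stated. A short named list of core parameters, with the rest descriptive, is one option and not the only one.

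Report the Bland-Altman limits of agreement with confidence intervals against the same limits.

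A limit fixed in advance does discriminate: the single-parameter pass probabilities under (d) fall from 0.978 to 0.0002 as the SD of the differences grows from 0.75 to 2 times the fixed SD. What must change is the size of the limit, which should reflect the difference that is acceptable between two methods.

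The cost is revised wording and one table. The downside is that the limits have to be agreed before any data are seen. No extra samples are needed.
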